5. GENERAL METHODOLOGY AND CONVENTIONS

5.1. Hypotheses and Decision Rules

The primary objective of the study is to estimate global prevalence of ATTR-CM in HFpEF participants. No formal hypotheses testing will be performed.

5.2. General Methods

5.2.1. Analyses for Prevalence Endpoints

The primary endpoint estimating prevalence will be evaluated by dividing the number of participants who are classified as ATTR-CM positive by Cardiac Scintigraphy as defined in [Section 3.1](#) by the total number of evaluable participants. The secondary endpoints estimating prevalence will be evaluated by dividing the number of participants who are classified as ATTR-CM positive by Cardiac Scintigraphy as defined in [Section 6.1.1.1](#) by the total number of HFpEF evaluable participants in the study (primary) or the relevant subgroup (secondary). Exact 95% confidence intervals for the prevalence estimates will be calculated using the method of Clopper and Pearson.¹

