3. OBJECTIVES AND ENDPOINTS

Primary Objective(s):	Primary Endpoint(s):
To assess the prevalence of ATTR-CM among patients with HFpEF within a clinically at-risk population.	Estimate of global prevalence of ATTR-CM in HFpEF patients. Diagnosis of ATTR-CM is defined as: 
• Cardiac Scintigraphy Grade 1, with confirmation of ATTR by cardiac biopsy, or:• Cardiac Scintigraphy Grade 2 or above.
Secondary Objective(s):	Secondary Endpoint(s):
To assess variations in prevalence of ATTR-CM (wild-type [WT] and hereditary) among patients with HFpEF at a country, regional, and global level.	
• Estimate of prevalence of ATTR-CM in patients with HFpEF based on:
• Geographical or regional distribution;• Age categories;• Gender.• Proportion of patients with WT and hereditary forms among patients diagnosed with ATTR-CM.• Baseline characteristics of HFpEF patients with and without ATTR-CM:
• New York Heart Association (NYHA) classification;• NT-proBNP.

CCI

CCI

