4. STUDY DESIGN

4.1. Overall Design

This study is a global, multi-center epidemiology study designed to estimate the global prevalence of ATTR-CM in participants with HFpEF within a clinically at-risk population. The study will enroll approximately 2000 patients.

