9. STATISTICAL CONSIDERATIONS

Detailed methodology for summary and statistical analyses of the data collected in this study will be documented and will be maintained by the sponsor.

The primary completion date (PCD) for the global prevalence estimate will be the date when all enrolled participants have either been diagnosed with ATTR-CM (scintigraphy grades 2 or 3), have scintigraphy grade 1 or found to be negative for ATTR-CM (scintigraphy grade 0) and have completed Follow-up Visit 1. Results will be reported after PCD and at the end of study (LPLV for participants with scintigraphy grade 1, 2 or 3).

The empirical estimate for the prevalence of ATTR-CM in HFpEF participants is approximately 10%. The study will enroll approximately 2000 HFpEF participants within whom it is expected to detect 200 ATTR-CM participants. Enrollment will be stopped if 200 ATTR-CM participants are identified before 2000 HFpEF are enrolled. No formal sample size calculation was performed. A sample size of 2000 HFpEF participants would be sufficient to inform treatment guidelines and yield an estimate for the global prevalence of ATTR-CM in HFpEF participants with a precision of $\pm 2.5\%$.

The primary endpoint is an estimate of the global prevalence of ATTR-CM in HFpEF participants. Diagnosis of ATTR-CM is defined as:

- Cardiac Scintigraphy Grade 1, with confirmation of ATTR by cardiac biopsy; or
- Cardiac Scintigraphy Grade 2 or above.

This global prevalence estimate will be obtained by dividing the number of participants who are diagnosed with ATTR-CM in the study by the total number of HFpEF participants evaluated. A 95% confidence interval on the estimate will also be calculated.

As secondary analysis, prevalence will be estimated for:

- Regions and countries.
- Age categories (60-64, 65-69, 70-74, 75-79, 80-85, >85).
- Gender (male, female).

Prevalence estimates along with 95% CI will be generated for regions and countries with at least 50 participants. For regions and countries that enroll fewer than 50 participants, prevalence will not be estimated. Regions will be defined in the statistical analysis plan. The proportion of HFpEF participants who were diagnosed with wild-type and variant ATTR-CM will be descriptively summarized.

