6. ANALYSES AND SUMMARIES

6.1. Primary Endpoint(s)

The primary endpoint is an estimate of the global prevalence of ATTR-CM in HFpEF participants. Diagnosis of ATTR-CM is defined as:

- Cardiac Scintigraphy Grade 1, with confirmation of ATTR by cardiac biopsy during the study period, or:
- Cardiac Scintigraphy Grade 2 or above.

The primary endpoint will be evaluated by dividing the number of participants who are classified as ATTR-CM positive by Cardiac Scintigraphy (as noted above) by the total number of HFpEF evaluable participants in the study. The proportion of Scintigraphy Grade 1 participants that are diagnosed with ATTR-CM will be estimated. Scintigraphy

Grade 1 participants that are diagnosed with ATTR-CM using a criteria other than cardiac biopsy and participants lost to follow-up without a confirmation of cardiac biopsy will be assumed as not diagnosed with ATTR-CM in the primary analysis. Exact 95% confidence intervals for the prevalence will be calculated using the method of Clopper and Pearson.¹ The primary analysis will be generated using the “Evaluable Analysis Set”.

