6.2. Secondary Endpoint(s)

The Secondary endpoints listed below will be compared between HFpEF participants with and without ATTR-CM as defined in [Section 6.1.1.1](#).

- The prevalence of ATTR-CM in HFpEF participants will be evaluated for subgroups including regions (North America, Europe, and Asia), age categories (60-64, 65-69, 70-74, 75-79, 80-85, >85), and gender (male, female). Exact 95% confidence intervals for the prevalence in subgroups will be calculated using the method of Clopper and Pearson.¹ Prevalence estimates along with 95% CIs will be generated for subgroups with at least 50 participants. For subgroups that enroll fewer than 50 participants, prevalence will not be estimated. These secondary analyses will be generated using the “Evaluable Analysis Set”.
- Participants diagnosed with ATTR-CM will be evaluated for TTR genotype, ie, wild-type or hereditary form. The proportions of these two genotypes will be evaluated as a secondary endpoint using descriptive statistics only (ie, number and percentage).
- NYHA classification proportions will be compared between HFpEF participants diagnosed with ATTR-CM and those that are not diagnosed with ATTR-CM using the Chi-square test. Fisher’s exact test will be used instead if any one of the cells has ≤ 5 participants. Proportion of NYHA classifications will also be descriptively summarized (frequency tables) by scintigraphy grade for participants who are diagnosed with ATTR-CM. Participants with non-evaluable scintigraphy grade will be summarized in a separate group.
- NT-proBNP will be compared between HFpEF participants diagnosed with ATTR-CM and those that are not diagnosed with ATTR-CM using a Wilcoxon rank sum test.

- NT-proBNP (mean, standard deviation, median, IQR, minimum and maximum) will be descriptively analyzed by scintigraphy grade and NYHA classification for participants who are diagnosed with ATTR-CM. Participants with non-evaluable scintigraphy grade will be summarized in a separate group.

CCI

CCI

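### The global prevalence interval assumes independent participants; if prevalence differs between sites it will be too narrow, and the SAP plans no site-clustered interval beside it

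*SAP*

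**What the plan says.** SAP 5.2.1 sets the general rule: "Exact 95% confidence intervals for the prevalence estimates will be calculated using the method of Clopper and Pearson". The primary estimate is a pooled proportion: participants classified as ATTR-CM positive are divided "by the total number of HFpEF evaluable participants in the study" (SAP 6.1). The same section adds: "Exact 95% confidence intervals for the prevalence will be calculated using the method of Clopper and Pearson". SAP 6.2 uses the same method for regions, age groups and gender, wherever a subgroup has at least 50 participants. Protocol Section 9 asks only for a 95% interval and names no method.

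Protocol 4.1 describes the design: "This study is a global, multi-center epidemiology study designed to estimate the global prevalence of ATTR-CM in participants with HFpEF". SAP 5.1 makes the study one of estimation: "No formal hypotheses testing will be performed".

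The available text of both documents mentions no site effect, clustering, ICC, design effect, robust variance or weighting. It also does not give the number of sites or of participants per site.

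**The concern.** Clopper-Pearson limits are exact when every participant is an independent draw with the same probability. Two features of the plan give reason to doubt this within a site:

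- **Entry.** Septal thickness (at least 12 mm) and ejection fraction are read by the site's own qualified reader (Protocol 5.1 and 8.2.2). Sites that read the threshold differently admit different mixes of patients.
- **Case status for Grade 1.** A Grade 1 scan counts in the primary numerator only with cardiac biopsy confirmation (SAP 6.1). Protocol 8.2.1 says such a participant should have a biopsy, but no study visit includes one, and results are collected only if it was done. Local biopsy practice therefore affects who is counted as a case.

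Positive correlation within sites raises the variance of the pooled proportion above the binomial value. The estimate and its interval are the whole primary result, so an interval that is too narrow overstates what the study has established about global prevalence.

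**Working it through.** **Inputs from the documents.** N = 2000, assumed prevalence p = 10%, so 200 expected cases; stated precision ±2.5 percentage points (Protocol Section 9); Clopper-Pearson limits (SAP 5.2.1).

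**Inputs assumed.** Between-site SD of true prevalence of 3, 5 or 7 points; 10, 20 or 40 participants per site (200, 100 or 50 sites); equal site sizes.

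**Step 1: the plan's own figure.** The normal half-width is 1.96 × √(0.10 × 0.90 / 2000) = 1.31 points. Clopper-Pearson for 200/2000 gives 8.72% to 11.40%, a half-width of (11.40 − 8.72)/2 = 1.34 points. The protocol's ±2.5 is not reproduced. It would correspond to a design effect of (2.5/1.315)² ≈ 3.6, but the protocol does not say one was intended, and no formal sample size calculation was done.

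**Step 2: ICC.** ICC = SD² / [p(1 − p)]:
- SD 3 points: 0.0009/0.09 = 0.010
- SD 5 points: 0.0025/0.09 = 0.028
- SD 7 points: 0.0049/0.09 = 0.054

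**Step 3: design effect and half-width.** DEFF = 1 + (m − 1) × ICC, with m participants per site; clustered half-width ≈ 1.34 × √DEFF. For m = 40 and SD 7: 1 + 39 × 0.0544 = 3.12, and 1.34 × √3.12 = 2.37. Coverage is that of the planned Clopper-Pearson interval in a beta-binomial simulation (20,000 runs per case).

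| Per site | SD (points) | DEFF | Half-width (points) | Clopper-Pearson coverage |
|---|---|---|---|---|
| 10 | 3 | 1.09 | 1.40 | 94–95% |
| 10 | 5 | 1.25 | 1.50 | 93% |
| 10 | 7 | 1.49 | 1.64 | 90% |
| 20 | 3 | 1.19 | 1.46 | 93–94% |
| 20 | 5 | 1.53 | 1.66 | 90% |
| 20 | 7 | 2.03 | 1.91 | 84% |
| 40 | 3 | 1.39 | 1.58 | 91% |
| 40 | 5 | 2.08 | 1.93 | 84% |
| 40 | 7 | 3.12 | 2.37 | about 75% |

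With no site variation, coverage is about 95.6%.

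**Step 4: does a clustered interval repair it?** The Korn-Graubard interval (Clopper-Pearson limits on the effective sample size) covers about 95–96% in these scenarios. With zero ICC its half-width is about 1.37 points against 1.34, so little is lost if clustering is absent.

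**Step 5: subgroups.** Coverage of Clopper-Pearson at p = 10%, for ICC 0.01 and 0.05 (site layouts assumed):

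| Subgroup | ICC 0.01 | ICC 0.05 |
|---|---|---|
| 500 (25 sites of 20) | 94.5% | 86.8% |
| 50 (5 sites of 10) | 96.3% | 93.5% |
| 50 (10 sites of 5) | 96.6% | 95.6% |

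With only 3 sites of 20, the Korn-Graubard half-width is about 17 to 23 points against about 8 for Clopper-Pearson. A site-robust Wald interval without small-sample correction covers only 67–70%.

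**The case against.** The strongest objection is that the size rests wholly on assumptions. At 200 sites and an SD of 3 points the loss is negligible. This stands, and it is why the point is conditional.

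A reader might take the secondary objective on geographic variation, "To assess variations in prevalence of ATTR-CM (wild-type [WT] and hereditary) among patients with HFpEF at a country, regional, and global level", as proof of correlation. It is an aim, not a finding. Stable differences between regions treated as fixed strata do not inflate the variance either: for prevalences of 5%, 10% and 15% in equal thirds, the mean of p(1 − p) is (0.0475 + 0.0900 + 0.1275)/3 = 0.0883, slightly below 0.0900. Only unexplained variation between sites matters here.

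Scintigraphy, the main determinant of case status, is graded centrally (Protocol 8.2.1). That removes site-reader effects on the grade, but not the entry reading or the biopsy practice.

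If the enrolled sites are themselves the whole target, the simple interval is not too narrow. The documents describe no sampling of sites and do not settle this. The endpoint is nevertheless called global and is meant to inform treatment guidelines (Protocol Section 9), which reaches beyond the enrolled sites.

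A reader might also infer that every regional interval is too narrow, or that the stated precision is missed. Neither is supported. Near the 50-participant floor, Clopper-Pearson's own conservatism can absorb a small ICC. Every equal-size scenario above stays within ±2.5 points.

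**Conclusion.** The point holds conditionally, for the global estimate. The planned interval ignores site clustering, and the documents contain plausible sources of it. If site prevalence varies by an SD of 3 to 7 points with 10 to 40 participants per site, true coverage lies between about 95% and 75%, and the half-width should be about 1.4 to 2.4 points instead of 1.34. Site numbers, site sizes and the ICC are assumptions; equal site sizes are also assumed. The protocol's stated precision is not threatened in these scenarios; what suffers is the honesty of the reported interval. No blanket statement about regional, age or gender intervals is justified. Should-fix, moderate confidence.

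**What to change.** In SAP 5.2.1 and 6.1:

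- Keep the simple ratio as the point estimate.
- Add a 95% interval for the global estimate with site as the cluster: Clopper-Pearson limits on the effective sample size (Korn-Graubard), with the effective size capped at n.
- Report it beside the simple Clopper-Pearson interval, with the number of contributing sites and the estimated ICC.

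In SAP 6.2, apply the clustered interval to a region or other subgroup only where a pre-stated minimum number of sites contributes. Otherwise keep Clopper-Pearson and state that it ignores site clustering. Do not use a site-robust GEE without small-sample correction where sites are few.

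The cost is SAP wording and a few lines of code, with no new data beyond the site identifier. The downside is a somewhat wider reported interval. SAP Section 2 says major changes to the primary analysis are also reflected in a protocol amendment. The team should record whether this addition, which leaves the estimate and the simple interval in place, counts as one.

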5.2.2. Analyses for Continuous Endpoints

All secondary **CCI** endpoints reported as numerical values will be analyzed descriptively using mean, standard deviation, median, IQR, minimum and maximum. Where applicable, secondary **CCI** endpoints of interest which specify comparisons between HFpEF participants diagnosed with ATTR-CM as defined in [Section 6.1.1.1](#) and those that are not diagnosed with ATTR-CM that are normally distributed will be compared using a t-test. Endpoints that are not normally distributed will be compared using the Wilcoxon rank sum test.

5.2.3. Analyses for Categorical Endpoints

Secondary endpoints that are categorical will be summarized descriptively using frequency tables. The Chi-square test will be used to compare the proportions between HFpEF participants diagnosed with ATTR-CM as defined in [Section 6.1.1.1](#) and those that are not diagnosed with ATTR-CM, where applicable. Fishers exact test will be used instead of the chi-square test if any one of the cells has ≤ 5 participants.

5.3. Methods to Manage Missing Data

No missing data imputation will be performed in the analyses described in [Section 6](#).

6. ANALYSES AND SUMMARIES

6.1. Primary Endpoint(s)

The primary endpoint is an estimate of the global prevalence of ATTR-CM in HFpEF participants. Diagnosis of ATTR-CM is defined as:

- Cardiac Scintigraphy Grade 1, with confirmation of ATTR by cardiac biopsy during the study period, or:
- Cardiac Scintigraphy Grade 2 or above.

The primary endpoint will be evaluated by dividing the number of participants who are classified as ATTR-CM positive by Cardiac Scintigraphy (as noted above) by the total number of HFpEF evaluable participants in the study. The proportion of Scintigraphy Grade 1 participants that are diagnosed with ATTR-CM will be estimated. Scintigraphy

Grade 1 participants that are diagnosed with ATTR-CM using a criteria other than cardiac biopsy and participants lost to follow-up without a confirmation of cardiac biopsy will be assumed as not diagnosed with ATTR-CM in the primary analysis. Exact 95% confidence intervals for the prevalence will be calculated using the method of Clopper and Pearson.¹ The primary analysis will be generated using the “Evaluable Analysis Set”.

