4.2. Scientific Rationale for Study Design

It has recently been described that ATTR amyloidosis is significantly underdiagnosed, taking into consideration that both the clinical presentation and the symptoms are non-specific. The most frequent form of HF in patients with ATTR-CM is HF with preserved left ventricular ejection fraction (HFpEF). The aim of this epidemiology study is to assess the prevalence of ATTR-CM in a clinically at risk HFpEF population. Inclusion of an age criteria of ≥ 60 years enables only at-risk HFpEF participants to be enrolled.

Definitive diagnosis of ATTR-CM may include invasive tissue biopsy. Extracardiac biopsy has a low diagnosis yield in ATTR amyloidosis, particularly in wild-type ATTR (ATTRwt). Therefore, in the setting of high clinical suspicion and a negative extracardiac biopsy, endomyocardial biopsy would be required. This invasive diagnostic approach carries

associated complications and delays in diagnosis.²² Alternatively, noninvasive cardiac scintigraphy has marked a crucial change in the diagnostic workup of the disease. Data show that a Grade 2 or 3 uptake, in the absence of monoclonal proteins on serum and urine immunofixation electrophoresis and serum free light chain assay, is associated with 100% sensitivity and 100% specificity for cardiac ATTR amyloidosis.²² In the case of Grade 1 uptake, histological confirmation through endomyocardial biopsy with typing of amyloid is required.

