8.2. Assessments

8.2.1. Scintigraphy

All participants will undergo radionuclide cardiac scintigraphy at Visit 1 with a bisphosphonate radiotracer: ^{99m}Tc -DPD, ^{99m}Tc -PYP, or ^{99m}Tc -HMDP. Cardiac retention of all ^{99m}Tc -DPD, ^{99m}Tc -PYP, or ^{99m}Tc -HMDP will be determined by the central reader according to the grading:

Grade 0=absent cardiac uptake.

Grade 1=mild uptake less than bone.

Grade 2=moderate uptake equal to bone.

Grade 3=high uptake greater than bone.

Details of scintigraphy will be provided in a separate laboratory manual (Scintigraphy manual).

To confirm a diagnosis of ATTR-CM a participant with Grade 1 scintigraphy should undergo an endomyocardial biopsy.^{20,32} If biopsy or other confirmatory testing is performed, data will be collected.

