8.2.6. Testing for Light Chain Amyloid

Specifications for testing samples are provided in the study laboratory manual. Blood and urine specimens for serum free light chains assay and the serum and urine electrophoresis with immunofixation will be obtained from all participants, but only analyzed for those with scintigraphy Grades 1, 2, or 3. As standard of care, participants with serum or urine test result indicative of monoclonal gammopathy of undetermined significance (MGUS) will require a confirmatory biopsy performed locally.

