3.4. Baseline Variables

This study does not have a study treatment and all assessment for the primary, secondary, and CCI endpoints, are collected either during the Screening Visit or Visit 1 (Day 1).

CCI

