6.1.1.1. Sensitivity/Supplementary Analysis

As a sensitivity analysis, the prevalence will be estimated using the diagnosis criteria described in the primary endpoint, but will include all participants with Scintigraphy Grade 1 diagnosed with ATTR-CM in the study (regardless of the cardiac biopsy). Specifically, participants with Scintigraphy Grade 1 that were diagnosed with ATTR-CM using a criteria other than cardiac biopsy will be included in the estimate of prevalence in this sensitivity analysis. Scintigraphy Grade 1 participants that are lost to follow-up prior to a diagnosis of ATTR-CM will be assumed as not diagnosed with ATTR-CM. The proportion of Scintigraphy Grade 1 participants that are diagnosed with ATTR-CM will be estimated.

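### Every Grade 2–3 scan counts as ATTR-CM, with no stated rule for a biopsy that types the amyloid otherwise and no visible analysis that bounds the effect

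*SAP*

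**What the plan says.** **Case definition.** Protocol 1.1, 3 and 9 and SAP 2.1 and 6.1 use the same two limbs: Grade 1 with confirmation by cardiac biopsy, or "Cardiac Scintigraphy Grade 2 or above". The second limb carries no condition. The primary completion date in Protocol 9 treats the scan as the diagnosis, since it refers to participants who "have either been diagnosed with ATTR-CM (scintigraphy grades 2 or 3").

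**Alternative definition.** SAP 6.1.1.1 keeps the primary criteria "but will include all participants with Scintigraphy Grade 1 diagnosed with ATTR-CM in the study (regardless of the cardiac biopsy"). It changes nothing at Grade 2–3. This definition also governs the secondary analyses (SAP 3.2, 6.2) and the adverse event summaries (SAP 6.4.1).

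**Accuracy cited.** Protocol 4.2 reports 100% sensitivity and specificity for "Grade 2 or 3 uptake, in the absence of monoclonal proteins on serum and urine immunofixation electrophoresis" and on the serum free light chain assay.

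**Tests run.** Under Protocol 8.2.6 light-chain samples are taken from everyone and analysed for Grades 1–3. The section adds: "As standard of care, participants with serum or urine test result indicative of monoclonal gammopathy of undetermined significance (MGUS) will require a confirmatory biopsy", done locally.

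**Collection of typing results.** Protocol 8.2.1 says: "If biopsy or other confirmatory testing is performed, data will be collected". The Schedule of Activities (1.4) marks subsequent diagnosis testing at a Follow-up 2 visit held for Grades 1–3. Sections 8.1.4 and 8.2.18 put the question to Grade 1 only.

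**The concern.** The accuracy figure that supports a scan-only diagnosis at Grade 2–3 is quoted for people without monoclonal proteins. The case definition drops that qualifier, although the study runs the tests that would apply it. If a participant has Grade 2–3 uptake, a monoclonal finding and a biopsy typed as non-ATTR, no visible text removes that participant from the numerator. Exclusion 5 covers only amyloidosis already diagnosed at entry. The Evaluable Analysis Set drops only non-evaluable scans.

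Such a participant would count in global prevalence, in the region, age and sex estimates, in the ATTR-CM group of the comparisons and safety summaries, and in a genotype split that offers only wild-type or hereditary. Enrolling more participants does not shrink an error of this kind. Grade 1 has an explicit rule for unconfirmed diagnoses and a sensitivity analysis. Grade 2–3, the limb counted without biopsy, has neither in the visible text.

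**Working it through.** **1. The plan's own figures.** Protocol 9 gives N = 2000 and prevalence of about 10%, so expected cases = 2000 × 0.10 = 200, as stated. The exact (Clopper-Pearson) 95% interval for 200/2000 is 8.72–11.40%. The normal-approximation half-width is 1.96 × √(0.10 × 0.90 / 2000) = 1.31 points, so the stated ±2.5 points is met with room to spare.

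**2. Effect of false cases.** Suppose all 200 cases are Grade 2–3 (a simplification), a share m is monoclonal-positive, and a share f of those is not ATTR. False cases k = 200 × m × f, and corrected prevalence = (200 − k)/2000. Each 1% of cases is 2 participants, and 2/2000 = 0.1 point. The documents give neither m nor f, so every value below is an assumption.

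| m, f | k | Corrected prevalence | Exact 95% CI |
|---|---|---|---|
| 5%, 0.5 | 5 | 9.75% | 8.48–11.13% |
| 5%, 1 or 10%, 0.5 | 10 | 9.50% | 8.25–10.87% |
| 10%, 1 or 20%, 0.5 | 20 | 9.00% | 7.78–10.34% |
| 20%, 1 | 40 | 8.00% | 6.85–9.28% |

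Five of the six (m, f) pairs stay inside 8.72–11.40%; only 8.00% falls outside. All six lie within 2.5 points of 10%.

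**3. Threshold.** 175/2000 = 8.75% is inside the lower limit of 8.72%; 174/2000 = 8.70% is outside. That takes 200 − 174 = 26 false cases, or 13% of 200. At the 13% prevalence quoted in Protocol 2.2, the 200-case stop would fall at 200/0.13 ≈ 1538 participants (13.0%, CI 11.36–14.79%). There 174/1538 = 11.31% is the first value outside, again 26 false cases.

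**4. Smallest reportable subgroup.** With 50 participants, one false case moves 5/50 = 10.0% (CI 3.33–21.81%) to 4/50 = 8.0%. That is 2.0 points, well inside the interval.

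**5. What a bound would look like.** Assume 20 monoclonal-positive participants among the 200 cases: 5 typed ATTR, 5 typed non-ATTR, 10 untyped. Counting the untyped as cases gives (200 − 5)/2000 = 9.75% (8.48–11.13%). Counting them as non-cases gives (200 − 15)/2000 = 9.25% (8.02–10.61%).

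**6. Would the typing be available?** Protocol 1.4 and 8.2.1 can be read to include Grade 2–3 results, although the 8.2.1 sentence follows one about Grade 1. Sections 8.1.4 and 8.2.18 ask only Grade 1. SAP 3.4 says primary and secondary assessments "are collected either during the Screening Visit or Visit 1 (Day 1"), which leaves out any later biopsy. That already conflicts with SAP 6.1, where Grade 1 biopsies during the study period count, so it shows nothing specific to Grade 2–3.

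**The case against.** Several stronger readings are tempting, and the documents do not support them.

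- **That the plan expressly keeps a biopsy-typed light-chain participant as a case.** No section says so. It follows from an unconditional rule with no stated override.
- **That Protocol 4.2 allows scan-only diagnosis solely when monoclonal proteins are absent.** It reports accuracy in that setting and does not rule out others. Protocol 2.2 calls the method highly sensitive and specific without stating the condition.
- **That participants known to be non-ATTR would sit in the numerator.** If collection is limited to Grade 1, the analysis would never learn of them. If it covers Grade 2–3, part of the data-capture criticism falls away.
- **That an MGUS-indicative result means light-chain amyloid.** Section 8.2.6 sends it for confirmation.
- **That reported prevalence is too high overall.** The Grade 1 rule pushes the other way: "participants lost to follow-up without a confirmation of cardiac biopsy will be assumed as not diagnosed with ATTR-CM in the primary analysis". The net direction is undetermined.
- **That the light-chain results are never used.** Much of the SAP endpoint and analysis text is redacted or not in the supplied text, and the PACL of 08 October 2021, on which the SAP is based, was not supplied.

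The strongest objection is on materiality. No rate is given, and most assumed scenarios stay inside the interval. That stands, and it limits the weight of the point. It does not remove the gap: the definition is fully visible in SAP 6.1 and 6.1.1.1, it departs from the condition attached to the cited accuracy, and nothing visible bounds the result.

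**Conclusion.** The point holds as a gap in the case definition that should be fixed. It is not a demonstrated error in the primary result. Applied as written, the rule can classify non-ATTR disease as ATTR-CM at Grade 2–3, with an error on that limb of zero or upward. The size cannot be derived: 0.1 point per 1% of 200 cases is arithmetic, while any actual share is an assumption, and 26 false cases would be needed to leave the planned interval. These figures treat all 200 expected cases as Grade 2–3. Confidence is high on the definition and moderate on the absence of any other use of the light-chain tests, because of the unseen text.

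**What to change.** These are changes to analysis definition and data recording. No test, biopsy or clinical rule is proposed.

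1. **Bound the limb.** Add a separately labelled sensitivity analysis to the SAP, giving prevalence with exact 95% CIs. Count Grade 2–3 participants with an MGUS-indicative result and no typed biopsy once as cases and once as non-cases. Report missing light-chain tests separately. This leaves the secondary definition unchanged.
2. **State the rule.** In SAP 6.1 and Protocol 1.1, 3 and 9, say that a Grade 2–3 participant whose recorded biopsy during the study period types the amyloid as non-ATTR is not a case and stays in the Evaluable denominator. Carry the sentence into SAP 6.1.1.1 and acknowledge that this, unlike item 1, also changes the secondary and safety definition.
3. **Reconcile collection.** Align Protocol 1.4 and 8.2.1 with 8.1.4 and 8.2.18, and SAP 3.4 with 6.1, so that typing results already obtained for Grade 2–3 are recorded.

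I would not alter the 200-case enrolment stop. Typing may arrive around Follow-up 2, months after the scan, so a clause there may have little effect.

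**Cost.** A SAP amendment, a short protocol amendment (SAP 2 requires one for a major change to the primary endpoint definition), and one data item at a Follow-up 2 contact that Grade 2–3 participants already have. Prevalence may come out slightly lower, and end-of-study figures may update those reported after the primary completion date. Item 2 reaches only participants who were biopsied and typed, so some upward error can remain among untyped monoclonal-positive participants; item 1 displays its possible size.

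### The primary prevalence interval carries sampling error only, and the Grade 2-3 numerator omits the monoclonal-protein condition on which the cited 100% scan accuracy depends

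*SAP*

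**What the plan says.** SAP 6.1 defines the estimate: "The primary endpoint will be evaluated by dividing the number of participants who are classified as ATTR-CM positive by Cardiac Scintigraphy", over the evaluable participants. Grade 2 or above is a case on the scan alone. Grade 1 is a case only with a confirming cardiac biopsy. Protocol Section 9, in defining the primary completion date, treats Grade 0 as negative for the disease. For uncertainty, SAP 6.1 says: "Exact 95% confidence intervals for the prevalence will be calculated using the method of Clopper and Pearson".

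The support for accepting Grade 2-3 without confirmation is in Protocol 4.2, where such uptake "is associated with 100% sensitivity and 100% specificity for cardiac ATTR amyloidosis". No sample size or interval is given. The same sentence limits the claim to people whose serum and urine immunofixation and serum free light chain assay show no monoclonal protein. Protocol 8.2.6 has these tests analysed for everyone with Grade 1, 2 or 3, and calls for a local confirmatory biopsy when the result suggests MGUS. Neither result enters the case definition in Protocol Sections 3 and 9 or in SAP 6.1.

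SAP 6.1.1.1 begins: "As a sensitivity analysis, the prevalence will be estimated using the diagnosis criteria described in the primary endpoint". It then changes one thing: Grade 1 participants diagnosed by a method other than cardiac biopsy are added. Grades 0, 2 and 3 are handled as before. No visible text in either document varies the accuracy of the scan.

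**The concern.** A Clopper-Pearson interval describes binomial sampling of a status that is taken as known. If some Grade 2-3 participants do not have ATTR-CM, or some Grade 0 participants do, the interval is centred on the wrong quantity, and a larger sample only narrows it around that quantity.

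The two kinds of error do not weigh equally. About 90% of those scanned are expected to be free of disease, so false positives come from a group nine times the size of the diseased group. The specificity of Grade 2 or above is therefore the quantity to examine.

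The one route to false positives that the documents themselves identify is monoclonal protein. The accuracy claim excludes such participants and the numerator does not. Prevalence is the only primary endpoint, and Protocol Section 9 expects the result to inform treatment guidelines, so readers should be able to see how far it depends on the scan being taken as correct.

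**Working it through.** **Inputs.** Protocol Section 9 gives a prevalence p of about 10% and says: "The study will enroll approximately 2000 HFpEF participants within whom it is expected to detect 200 ATTR-CM participants". The interval is two-sided 95% exact (SAP 6.1). Values of sensitivity (Se) and specificity (Sp) below 100% are assumptions, because the documents give none.

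**Step 1: sampling precision.**
- Normal approximation: 1.96 × √(0.10 × 0.90 / 2000) = 0.0131, or ±1.3 points.
- Clopper-Pearson for 200/2000: 8.72% to 11.40%.
- Protocol Section 9 states ±2.5%. That is met with room to spare but is not reproduced. It would need only 1.96² × 0.09 / 0.025² ≈ 553 participants.

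**Step 2: effect of misclassification.** Apparent prevalence = Se × p + (1 − Sp) × (1 − p).
- One lost point of specificity adds 0.01 × 0.90 = 0.90 points.
- One lost point of sensitivity subtracts 0.01 × 0.10 = 0.10 points.
- Loss of specificity equal to the sampling half-width: 1.31 / 0.90 ≈ 1.5 points.
- Loss equal to the stated ±2.5%: 2.5 / 0.90 ≈ 2.8 points.

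With true prevalence 10%, Se 100% and N = 2000, false positives number 2000 × 0.90 × (1 − Sp). Coverage is the exact binomial probability that the Clopper-Pearson interval contains 10%.

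| Assumed Sp | False positives | Apparent prevalence | Coverage of the true 10% |
|---|---|---|---|
| 100% | 0 | 10.00% | 96% |
| 99.5% | 9 | 10.45% | 91% |
| 99% | 18 | 10.90% | 75% |
| 98% | 36 | 11.80% | 28% |
| 97% | 54 | 12.70% | 4% |

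**Step 3: correcting an observed 10%.** Rogan-Gladen: (observed + Sp − 1) / (Se + Sp − 1).
- Se 100%, Sp 99%: 0.09 / 0.99 = 9.1%.
- Se 100%, Sp 98%: 0.08 / 0.98 = 8.2%.
- Se 100%, Sp 97%: 0.07 / 0.97 = 7.2%.
- Se 95%, Sp 100%: 0.10 / 0.95 = 10.5%.
- Se 90%, Sp 100%: 0.10 / 0.90 = 11.1%.
- Se 90%, Sp 99%: 0.09 / 0.89 = 10.1%. Here the two errors nearly cancel.

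**Step 4: the monoclonal-protein condition.** The documents do not say how many Grade 2-3 participants will have a positive light-chain test. Each one reclassified as a non-case lowers the estimate by 1/2000 = 0.05 points. About 26 of the expected 200 (0.0131 × 2000) would equal the sampling half-width.

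**The case against.** The strongest reply is that nothing in the documents shows specificity below 100%. Scintigraphy is described as a validated non-biopsy method (Protocol 2.2), grading is by a central reader (Protocol 8.2.1), and the endpoint is prevalence under a stated diagnostic definition, with no hypothesis test. Anyone could also apply the correction afterwards from the published count and denominator. Most of this stands. It makes the grid an illustration under assumptions and keeps the remedy supplementary. It does not answer the dropped condition, because outside readers cannot apply that without the participants' light-chain results.

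Two stronger readings are tempting and not supported.
- A reader might infer that even a small false-positive rate moves the estimate outside the reported interval. It does not: at 99% specificity an observed 10% corrects to 9.1%, inside 8.72% to 11.40%.
- A reader might infer that, by admitting biopsy-confirmed Grade 1 cases, the protocol contradicts its own accuracy figure and so casts doubt on specificity. That argument bears on sensitivity, where the effect is only 0.10 points per point. Protocol 4.2 also goes on to require histology for Grade 1.

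A fair technical objection is that Rogan-Gladen assumes one test with one pair of accuracy values, while the case definition is composite. Its effective sensitivity depends on how many Grade 1 participants are biopsied, which may differ by region. The grid must therefore be defined for the composite rule and kept to the global estimate. Corrected values can also fall below zero: at specificity 0.97 this happens when apparent prevalence is under 3%.

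**Conclusion.** The point holds in bounded form. The primary interval expresses sampling error only, and the accuracy claim behind it is conditional on a test result that the numerator ignores. How much bias follows, if any, is unknown from the documents. On the assumed scale, about 1.5 points of lost specificity would equal the ±1.3-point sampling half-width at 10% prevalence and N = 2000, with sensitivity held at 100%. Lost sensitivity works the other way at about one ninth of that rate. Over specificity 0.97 to 1.00 and sensitivity 0.90 to 1.00, an observed 10% corrects to between 7.2% and 11.1%. This is a cheap improvement to the reporting of the result and gives no reason to change the primary estimate.

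**What to change.** Add to SAP 6.1.1.1, leaving SAP 6.1 unchanged:

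1. A supplementary prevalence estimate in which Grade 2-3 participants count as cases only when the monoclonal-protein condition of Protocol 4.2 is met or a biopsy result confirms ATTR. Use the light-chain results and any biopsy results already collected. State in advance how missing light-chain results and positive results without a biopsy are classified, and report how many there are. Protocol 8.1.4 and 8.2.18 ask about later testing only for Grade 1, so biopsy data for Grade 2-3 may be incomplete.
2. A Rogan-Gladen table for the global estimate over a prespecified grid, for example specificity 0.97 to 1.00 and sensitivity 0.90 to 1.00, both defined for the composite case definition. Truncate corrected values at zero and label the table as assumption-based.

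No new data are needed. The cost is one extra table and a wider stated uncertainty beside the primary result.
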